1.2. Study Schematic: On-study Participant Progression

*NOTE: Release from quarantine is foreseen at Day 12 in case no virus is detected by the nasal RSV discharge test and the participant has no clinically significant symptoms. If the participant continues to have clinically significant symptoms and/or detectable virus on Day 12, additional extended quarantine stay may be required at the discretion of the Investigator.

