g	Samples for related exploratory research.

h	Upper respiratory tract swab (e.g. nasopharyngeal swab, mid-turbinate swab, oropharyngeal swab) for respiratory virus screen to assess for the presence of other respiratory viruses; if found positive for any pathogen in the panel, the participant will not be eligible for the current quarantine. Sample will also be tested for SARS-CoV-2 (COVID-19), which would contraindicate the participant's participation.
i	Pre-inoculation nasal samples are optional under PI discretion. Post inoculation Nasal virology samples will be collected at the same time each day during quarantine (\pm 1 hour) and used for RT-qPCR and viral culture assay (as appropriate). Samples may be used for related exploratory research.
j	Can be performed on Study Day -2 or Study Day -1.
k	Solicited reactogenicity will be collected from vaccination until 7 days after vaccination.
l	Unsolicited AEs will be collected from vaccination until 30 days after vaccination.
m	Blood serum pregnancy test (β-HCG) will be performed in all female participants who have been tested positive for urine pregnancy testing.
n	Assessments to be made pre and post dosing.
o	Participants will be closely observed for a minimum of 30 minutes post-vaccination. Any unsolicited, solicited AEs, and vital signs will be documented by the Investigator following this observation period.
p	Sample will be taken on Day -2, Day-1 or Day 0 pre-challenge.
q	Nasal sample for RSV discharge test will be collected on Day 11 or Day 12. A repeat test may be requested at PI discretion at subsequent days.
r	Sample collected only for subjects who consented to genetic testing. If a Day -28 sample is not taken, then it may be taken on the clinic visit 1 day post vaccination instead.
Notes:	Parenthesis indicates the assessment may be optional (will be identified in the Research Plan), or at the PI's discretion. The PI may perform additional safety assessments as required. For all participants TDS assessments will commence on Day 0, the first assessment will be pre-virus challenge. Where any nasal sampling time points occur together, the order of sampling will typically be (1) Nasosorption followed by (2) Nasopharyngeal swab followed by (3) Nasal wash.

GENOMIC, TRANSCRIPTOMIC AND PROTEOMIC SAMPLES				
	Yes		No	
DNA/RNA/proteomic sample collection:		DNA RNA. Proteomic.		

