Transmission of RSV to participants' close contacts	
RSV virus in nasal secretions can cause infection in close contacts.
 
Passing the RSV Challenge Virus to others, including vulnerable people (see below for definition of vulnerable populations).
	
Virus is usually absent from the nose by the time participants are discharged from quarantine. This will be confirmed by testing a nasal sample using a viral diagnostic (e.g. RVAT, PCR) to determine participants' suitability for departure.
 
Participants will remain in individual isolated rooms in the quarantine unit for 12 days after inoculation with the challenge virus.

Potential Risk of Clinical Significance	Rationale for Risk	Mitigation Strategy
		To reduce the risk of transmitting the virus into the community, participants will be asked to avoid, where possible, contact with vulnerable people for 14 days after they leave quarantine (Section 2.2.1.1).
	Passing the RSV Challenge Virus to study staff.	Clinic staff in contact with participants in the quarantine unit will require to wear Personal Protective Equipment (PPE) to avoid the transmission of the RSV Challenge Virus to study staff and to prevent the risk of cross-contamination by a viral disease being brought up into the unit by staff.
Risk of reactivation of herpes infection.	If a participant ever had a herpes infection (e.g., cold sores, genital herpes or shingles), there is a small possibility that this infection could return after challenge.	Participants will be instructed to inform the study staff if they currently have an active herpes infection or have had one during the 30 days before enrolment.
Please consult the IB for detailed information.		

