Participants will reside in the Quarantine Unit for a total of approximately 15 days (from Day -2 to Day 12). From Day 2 to Day 11, nasal samples will be collected approximately every 12 hours, and physical examination, vital signs measurements, ECG, clinical safety laboratory test, and Spirometry will be performed as per the Schedule of Activities (SOA) in [Section 1.3](#). Release from quarantine is foreseen at Day 12, provided no virus is detected (by either the qualitative virus antigen test (RVAT) or equivalent viral test, as appropriate) and the participant has no clinically significant symptoms. If the participant continues to have clinically significant symptoms and/or detectable virus on Day 12, additional extended quarantine stay may be required based on the assessment of the Investigator. If appropriate, participants may reside in quarantine for an additional night or longer before discharge.

Participants will attend a follow up visit at 28 days post-challenge (Day 28), and a follow-up visit at 6 months post-vaccination.

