8.16.2. Rapid Viral Antigen Test

A rapid diagnostic test (e.g. RVAT) will be used to determine the presence of RSV in a nasal sample taken prior to discharge from the Quarantine Unit on Day 12. (and subsequent days if, at the discretion of the PI, an extended quarantine stay is required due to test result and/or the presence of clinical symptoms) A PCR screening test may be used as an alternative test for this purpose.

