9.6.5. Primary Efficacy Analysis

The primary efficacy analysis of the primary endpoint family (as specified below) will be performed on the ITTc Analysis Set.

- The AUC for RSV-A Memphis 37b viral load measured in nasal samples by RT-qPCR, as determined by qRT-PCR on nasal samples collected twice daily starting two days post-viral challenge (Day +2) up to discharge from quarantine, will be summarised and RSVpreF compared to placebo via a t-test or Wilcoxon Rank-Sum test as appropriate.
- Symptomatic RSV infections will be summarised and RSVpreF compared to placebo using a chi-squared test. RT-PCR-confirmed symptomatic RSV infection, defined as:
 - RT-PCR-confirmed RSV infection (two detectable qRT-PCR measurements (reported on 2 or more consecutive days), starting two days post-viral challenge (Day +2) up to discharge from quarantine.), AND
 - Either one or more positive clinical symptoms of any grade from two different categories in the symptom scoring system (Upper Respiratory, Lower Respiratory, Systemic), or one Grade 2 symptom from any category.
- Sum total symptoms, as measured by graded symptom scoring system collected three times daily starting one days post-viral challenge (Day +1) up to discharge from quarantine, will be summarised and RSVpreF compared to placebo using a t-test or Wilcoxon Rank-Sum test as appropriate.

The primary efficacy analysis will be supported by sensitivity analyses and these will be specified in the SAP.

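### The primary sum total symptoms score is given two different end points, and the one tied to discharge lets the summing window depend on the outcome

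*Combined protocol and SAP*

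**What the plan says.** **End of the symptom sum.** Section 9.6.5 defines the primary sum total symptoms score from three-times-daily diary cards, "starting one days post-viral challenge (Day +1) up to discharge from quarantine". The endpoint tables in Synopsis 1.1 and Section 3 use the same end point. The Statistics part of the Synopsis, which describes the same endpoint for sample size, ends the sum at and including the Day +12 morning card. Section 9.2 repeats the sample-size assumptions but gives no window.

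**When discharge happens.** Section 4.1 states: "Release from quarantine is foreseen at Day 12, provided no virus is detected", and it also requires that the participant has no clinically significant symptoms. If either condition fails, "additional extended quarantine stay may be required based on the assessment of the Investigator". The note to Section 1.2 says the same: "additional extended quarantine stay may be required at the discretion of the Investigator".

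**What is collected in a longer stay.** Section 8.11.2 has diary cards completed three times a day during quarantine. Section 8.13 states that tissue distribution and collection go on until final discharge. The secondary endpoints for mucus weight and tissue number run from Day +1 to discharge.

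**Other cumulative endpoints that run to discharge.** These are TSS-AUC, VL-AUC by qRT-PCR (primary) and VL-AUC by viral culture. Section 4.1 schedules the twice-daily nasal samples only from Day 2 to Day 11.

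**The concern.** One primary endpoint has two definitions that agree only for participants who leave on Day 12 as planned. For anyone kept longer they give different totals, and the protocol does not say which governs.

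The discharge definition also has a structural weakness. A stay is prolonged because of symptoms or detectable virus, so the period over which symptoms are added up depends on the illness being measured. If the vaccine works, prolonged stays should fall mostly in the placebo arm. Their additional diary cards, mucus and tissues would then enlarge the difference in totals, partly because those participants were observed for longer. A total is comparable between arms when everyone is counted over the same period.

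**Working it through.** **1. The plan's own figure.** Inputs from Section 9.2: 31 per arm, 80% relative reduction, CV 113.55%, one-sided 5%.

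- Normal approximation: z = (0.80 / 1.1355) × √(31/2) − 1.645 = 0.7045 × 3.937 − 1.645 = 1.129, so power is 87.1%.
- Noncentral t: 86.4%.

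Both meet the stated minimum of 80%. This calculation does not involve the length of the window.

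**2. Scheduled diary cards.** Day +1 to Day +11 at three a day, plus one on the morning of Day +12: 11 × 3 + 1 = 34. As far as its columns can be read, the diary row of the Schedule of Activities agrees: three times daily to Day 11 and a single entry on Day 12.

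**3. Cards added by a longer stay.** Each extra full day adds 3 cards. The documents do not give the length of extended stays, so 1 to 3 days is an assumption.

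| Extra days | Cards | Increase |
|---|---|---|
| 1 | 37 | 3/34 = 8.8% |
| 2 | 40 | 6/34 = 17.6% |
| 3 | 43 | 9/34 = 26.5% |

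**4. Tissue collection.** Day +1 08:00 to Day +12 08:00 is 11 periods of 24 hours. One more day adds 1/11 = 9.1% collection time.

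Steps 3 and 4 count observation time for a retained participant. They do not measure how much the score rises.

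**5. Effect on the arm comparison (illustration).** The documents do not say how many participants stay longer, so the following are assumptions:

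- Scores are gamma distributed with CV 113.55%, 31 per arm, 20,000 simulated trials.
- 10% or 20% of placebo participants stay 1 or 2 extra days. They are drawn by a blinded coin-flip from the highest 20% or 40% of placebo scores, and the same score threshold applies in the vaccine arm.
- Symptoms on extra days equal the participant's own average. This is probably an upper bound.

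| Quantity | Fixed window | Window to discharge |
|---|---|---|
| Placebo mean (relative) | 0.999 | 1.024 to 1.070 |
| Apparent reduction, truth 50% | 50.0% | 50.6% to 51.4% |
| Apparent reduction, truth 80% | 80.0% | 80.5% to 81.1% |
| One-sided type I error | 4.9% | 4.9% |
| Power, truth 50% | 74.8% | 74.4% to 74.8% |

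The placebo mean rises by 2.5% (1.024/0.999) to 7.1% (1.070/0.999). The reduction is overstated by at most 1.4 percentage points.

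**The case against.** **The schedule already implies Day +12.** The Schedule of Activities appears to give one diary entry on Day 12, which matches the Synopsis sample-size text, and Section 8 makes adherence to the schedule required. Only tissues have an explicit sentence about extended stays. The detailed SAP announced in Sections 9.1 and 9.5 is not in the document reviewed and may settle the window. This stands as evidence of intent and supports Day +12 am as the right end point. It does not remove the discharge wording from the endpoint tables and Section 9.6.5.

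**The bias is small.** Section 2 and Section 2.2.1 say that illness in healthy adults usually resolves within 7 to 10 days, so late scores should be low. Participants released on time have no clinically significant symptoms, so little is missed after they leave. Symptoms recorded in a longer stay are real illness. Under Section 6.3 the Investigator and clinical staff are blinded, so without a vaccine effect extended stays do not favour an arm. All of this stands and limits the size of the point.

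**A stronger reading: release after a positive test is uncontrolled.** A reader might infer this from the Investigator's discretion and from note q to the schedule ("A repeat test may be requested at PI discretion at subsequent days"), and might ask for mandatory re-testing and confinement. The documents do not support that:

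- Section 4.1 makes planned Day 12 release conditional on no virus and no clinically significant symptoms.
- Section 8.16.2 provides for the discharge test on later days if, "at the discretion of the PI, an extended quarantine stay is required due to test result and/or the presence of clinical symptoms".
- Section 2.2.1 says virus is usually absent by discharge and commits to a test of suitability for departure. It does not promise that every participant leaves with a negative result. It adds that "participants will be asked to avoid, where possible, contact with vulnerable people for 14 days after they leave quarantine".

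How long to confine a healthy volunteer is a clinical trade-off for the Investigator. Written release criteria would be at most an optional clarification.

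**Conclusion.** The point holds as an inconsistency with a minor bias attached. The protocol ends one primary endpoint in two places. Under the discharge wording, a retained participant contributes 8.8% more diary cards per extra day than the scheduled 34. Mucus weight and tissue count gain 9.1% more collection time per extra day.

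A reader might infer that the primary test is invalid or that the vaccine effect would be materially exaggerated. The documents and the check do not support this. Blinded discharge leaves the type I error at 4.9% in the illustration, power for a true 50% reduction changes by at most 0.4 percentage points, and the estimate moves by about 1 point. Those figures rest on assumed retention of 10% to 20% of placebo participants for 1 to 2 days. The conflict between the two definitions rests on the text alone.

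**What to change.** 1. In Synopsis 1.1 (endpoint table), Section 3 and Section 9.6.5, end the sum total symptoms score at the Day +12 am diary card for every participant, whatever the discharge date. This adopts the sponsor's own sample-size definition.
2. In Synopsis 1.1 and Section 3, end total mucus weight and tissue count at the Day +12 08:00 collection. Section 8.13 can continue collection to final discharge.
3. Apply the same Day +12 cut-off to TSS-AUC, qRT-PCR VL-AUC and culture VL-AUC, so that totals from the same cards or samples share one window.
4. List data from extended stays separately and leave them out of these totals. Carry the same windows into the SAP.

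The cost is wording. No procedure, visit, sample or participant is added, and the Investigator's discretion over release is unchanged.

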4.2. Scientific Rationale for Study Design

The study will be conducted by hVIVO Services Limited, which has extensive experience with RSV challenge studies. Numerous studies have been performed using experimental RSV infection in human participants. To date, in hVIVO's studies, over 1300 participants have been successfully and safely inoculated with RSV-A Memphis 37b strain. These studies demonstrated that adults could be infected by

nasal inoculation and that experimental infection was safe. This RSV-A Memphis 37b strain has been shown to cause symptoms and virus shedding that closely match natural infection in healthy adults.

Administration of study intervention and challenge with RSV-A Memphis 37b strain will take place in hVIVO's specialised Clinical Units, either in the Quarantine Unit or Screening Clinic Units. Standard study procedures (including collection of blood, urine, and nasal secretions for assessment of safety and efficacy) have been employed in previous studies conducted by hVIVO.

Further details of study rational are included in [Section 2.1](#).

4.3. Justification for Dose

Three studies have compared different dose levels and formulations of RSVpreF.

- The first-in-human (FIH) study in adults 18 to 85 years of age evaluated the safety, tolerability, and immunogenicity of 3 escalating dose levels of 60 µg, 120 µg, and 240 µg, with or without Al(OH)₃, when administered alone or concomitantly with seasonal inactivated influenza vaccine (SIIIV) (C3671001).
- A study in older adults 65 to 85 years of age evaluated safety, tolerability and immunogenicity of 60 µg, 120 µg, and 240 µg RSVpreF doses formulated with Al(OH)₃ or CpG/Al(OH)₃- adjuvant ,or 240 µg RSVpreF with RSV antigens alone , when administered concomitantly with SIIIV (C3671002).
- A study in pregnant women 18 to 49 years of age evaluated safety tolerability and immunogenicity of 120 µg and 240 µg RSVpreF dose levels with and without Al(OH)₃ (C3671003).

In none of these studies were substantial differences between the immunogenicity or reactogenicity of 120 mg and 240 mg dose levels or of formulations with and without Al(OH)₃ observed. Therefore, 120 mg without Al(OH)₃ is chosen for the human challenge study.

4.4. End of Study Definition

A participant is considered to have completed the study if he/she has completed all phases of the study including the last scheduled procedure shown in the SoA or the last unscheduled visit as applicable. If a safety visit is required after the last scheduled visit, this will be at the PI's discretion as a duty of care, e.g., repeat spirometry or laboratory tests. These discretionary follow-up visits will not be considered part of the trial data unless they represent follow-up and closure on an AE or serious adverse event (SAE) identified during the trial period.

The end of the study is defined as the date of the last visit of the last participant in the study.

5. Study Population

Prospective approval of protocol deviations to recruitment and enrolment criteria, also known as protocol waivers or exemptions, is not permitted.

5.1. Inclusion Criteria

Participants are eligible to be included in the study only if all of the following criteria apply:

NO	STANDARD INCLUSION CRITERIA
To be eligible for the study, participants must meet all the following inclusion criteria:	
1	An informed consent document signed and dated by the participant and the Investigator.
2	Aged between 18 and 50 years old on the day of signing the consent form.
3	In good health with no history, or current evidence, of clinically significant medical conditions, and no clinically significant test abnormalities that will interfere with participant safety, as defined by medical history, physical examination, (including vital signs), ECG, and routine laboratory tests as determined by the Investigator.
4	A documented medical history prior to enrolment.
5	
The following criteria are applicable to female participants participating in the study.
 
a) Females of childbearing potential must have a negative pregnancy test prior to enrolment.
 
b) Females of non-childbearing potential:
 
 a. Post-menopausal females; defined as having a history of amenorrhea for >12 months with no alternative medical cause, and /or by FSH level >40mIU/mL, confirmed by laboratory. b. Documented status as being surgically sterile (e.g. tubal ligation, hysterectomy, bilateral salpingectomy and bilateral oophorectomy).
6	
The following criteria apply to female and male participants:
 
a) Female participants of childbearing potential must use one form of highly effective contraception. Hormonal methods must be in place from at least 2 weeks prior to the first study visit. The contraception use must continue until 28 days after the date of viral challenge/last dosing with IMP (whichever occurs last). Highly effective contraception is as described below:
 
 a. Established use of hormonal methods of contraception described below (for a minimum of 2 weeks prior to the first study visit). When hormonal methods of contraception are used, male partners are required to use a condom with a spermicide: 
 i. combined (oestrogen and progestogen containing) hormonal contraception associated with inhibition of ovulation:

NO	STANDARD INCLUSION CRITERIA
To be eligible for the study, participants must meet all the following inclusion criteria:	
	
1. oral
 
2. intravaginal
 
3. transdermal
 
ii. progestogen-only hormonal contraception associated with inhibition of ovulation:
 
1. oral
 
2. injectable
 
3. implantable
 
b. Intrauterine device (IUD)
 
c. Intrauterine hormone-releasing system (IUS)
 
d. Bilateral tubal ligation
 
e. Male sterilisation (with the appropriate post vasectomy documentation of the absence of sperm in the ejaculate) where the vasectomised male is the sole partner for that woman.
 
f. True abstinence - sexual abstinence is considered a highly effective method only if defined as refraining from heterosexual intercourse during the entire period of risk associated with the study treatments. The reliability of sexual abstinence needs to be evaluated in relation to the duration of the clinical trial and the preferred and usual lifestyle of the participant.
 
b) Male participants must agree to the contraceptive requirements below at entry to quarantine and continuing until 28 days after the date of Viral challenge / last dosing with IMP (whichever occurs last):
 
a. Use a condom with a spermicide to prevent pregnancy in a female partner or to prevent exposure of any partner (male and female) to the IMP.
 
b. Male sterilisation with the appropriate post vasectomy documentation of the absence of sperm in the ejaculate (please note that the use of condom with spermicide will still be required to prevent partner exposure). This applies only to males participating in the study.
 
c. In addition, for female partners of child bearing potential, that partner must use another form of contraception such as one of the highly effective methods mentioned above for female participants.
 
d. True abstinence - sexual abstinence is considered a highly effective method only if defined as refraining from heterosexual intercourse during the entire period of risk associated with the study treatments. The reliability of sexual abstinence needs to be evaluated in relation to the duration of the clinical trial and the preferred and usual lifestyle of the participant.
 
c) In addition to the contraceptive requirements above, male participants must agree not to donate sperm following discharge from quarantine until 28 days after the date of Viral Challenge/last dosing with IMP (whichever occurs last).

7	Sero-suitable to the challenge virus, as defined in the study Analytical Plan.

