2.2.1. Risk Assessment

The known risks to participants are detailed below. However, there may also be risks that are unforeseen and not anticipated (e.g., unknown allergies). Every effort will be made to monitor the health of the participants to ensure that such risks are minimised. Trained medical personnel and facilities will be available to provide medical emergency care.

During a pandemic, additional potential risks to participants may include interruptions to study visit schedule, adherence to protocol-specified safety monitoring or safety laboratory assessments. Refer to COVID-19 Crisis Management Plan for further details on the risks and risk mitigation strategy.

Potential Risk of Clinical Significance	Rationale for Risk	Mitigation Strategy
Study Intervention		
Intramuscular Dosing with RSVpreF	Prior studies showed RSVpreF to have an acceptable safety profile as described in Section 2. Signs and symptoms observed after vaccination with RSVpreF include fatigue/tiredness, muscle pain, headache, and joint pain. These were mild or moderate.	These potential reactions, if they are observed, will be monitored but are generally short-term and do not require treatment.
	Local signs and symptoms associated with the injection may include erythema, swelling/induration, and pain/tenderness at the injection site.	Local reactions will be monitored but are generally short-term and do not require treatment.
	Systemic exposure to RSVpreF	To minimise any risks associated with systemic exposure to RSVpreF, male and female participants must be on highly effective contraception methods during the study as described in Section 5.1 .
General Risks related to Vaccines	General signs and symptoms associated with administration of a vaccine, or vaccination with placebo, including fatigue, headache, myalgia, arthralgia, chills and nausea.	These side effects will be monitored but are generally short-term and do not require treatment.

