4.1. Overall Design

This is a randomised, Phase 2a, double blind, placebo-controlled study to evaluate the safety, immunogenicity and efficacy of an RSV vaccine against RSV-A Memphis 37b infection in healthy participants.

The total duration of study participation for a participant is approximately 6 months after vaccination, with the following sequence and duration of study periods:

Screening Phase:

- Screening prior to vaccination from Day -84 to Day -29 (Day -118 for RSV serology) Pre-screening data collected through the hVIVO generic screening process prior to signing the study specific consent form, and prior to vaccination from Day -84 to Day -29 (Day -118 for RSV serology) may be transferred to this study after study-specific consent form has been signed by the participant. Pre-screening data obtained prior to this window can be re-assessed any time prior to vaccination from Day -84 to Day -29.

Vaccination Phase:

- Vaccination on Day -28 (± 3 days), participants will be randomised 1:1 to receive RSVpreF or placebo
- Follow up clinic visit 1 day post vaccination
- Follow up clinic visit 7 days post vaccination (± 1 day)

Quarantine Phase:

- Admission to the Quarantine Unit on Day -2/-1; resident in the Quarantine Unit for approximately 15 days, from admission on Day -2 to planned discharge on Day +12.
- Challenge with Challenge Virus on Day 0.
- Discharge from quarantine planned on Day +12

Follow-Up Phase:

- Day +28 (± 3 days).
- Day +155 (± 14 days)

Participants will be pre-screened for susceptibility to RSV infection, i.e., have levels of RSV neutralising antibodies compatible with susceptibility to RSV infection.

Participants will be randomised to receive a single intramuscular dose of RSVpreF or Placebo on Day -28 (± 3 days):

- **Reference article product**
 - PF-06928316 also known as RSVpreF
 - Dose: 120mcg

- **Placebo product**

- Placebo to match vaccine

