6.1. Study Intervention(s) Administered

Table 1 Study Interventions

Intervention Name	RSVpreF	Placebo	RSV-A Memphis 37b virus]
Type	Biologic	Other	Virus
Dose Formulation	The active ingredients in RSVpreF are 2 stabilized RSV prefusion F antigens, in equal amounts from virus subgroups A and B, in a lyophilized dosage form for reconstitution. The drug product is supplied as a lyophilized white cake in a 2-mL glass vial, with a 13-mm lyophilization stopper, aluminum overseal, and flip-off cap. The drug product will be reconstituted by a diluent consisting of sterile water in a prefilled syringe (PFS).	Placebo will be a lyophile match to the vaccine, which will consist of excipients matched to those used in the RSVpreF formulation, minus the active ingredients. The physical appearance of the reconstituted RSVpreF and placebo will be matched, and the study will be conducted in a double-blinded manner.	Cryovial, Liquid
Unit Dose Strength(s)	120mcg vial	0.5mL/vial	The inoculum virus titre is determined in an infectivity (plaque) assay, the titre is reported in plaque forming units per mL (PFU/mL). The challenge dose is approximately $4.5\log_{10}$ PFU.
Dosage Level(s)	A single unit dose of 120 mcg RSVpreF will be reconstituted with sterile water for an 0.5 mL injection volume	The fill volume of the placebo vial and diluent prefilled syringe is designed that the intended dose is delivered in a 0.5 mL injection volume.	A single dose of virus will be delivered. Dose volume delivery method is provided in the Analytical Plan (AP).
Route of Administration	Intramuscular injection in left arm	Intramuscular injection in left arm	Intranasal
Use	Experimental reference article	Placebo control	Infectious challenge agent

IMP and NIMP	IMP	IMP	NIMP challenge virus
Sourcing	[REDACTED]	[REDACTED]	[REDACTED]
Packaging and Labelling	The details of the study intervention packaging and labelling will be provided in the study-specific Pharmacy Manual.	The details of the study intervention packaging and labelling will be provided in the study-specific Pharmacy Manual.	RSV Challenge Inoculum will be provided in vials. The details of the virus challenge agent packaging and labelling will be provided in the AP
Current/Former Name(s) or Alias(es)	n/a	n/a	n/a

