7.2. Participant Discontinuation

Participants will be withdrawn from study intervention for the reasons listed below. These participants must not receive any additional intervention but should continue to be followed for safety. Additional unscheduled visits may be performed for safety reasons.

- Non-compliance with the study requirements and restrictions.
- Clinically significant abnormal laboratory findings, which in the opinion of the Investigator(s) and/or Sponsor, precludes further participation in the study.
- Development of inter-current illness which, in the opinion of the Investigator would compromise the health of the participant or the study objectives.
- The Investigator's decision that withdrawal from further participation would be in the participant's best interest.
- Termination of the study at the discretion of the Investigator(s) or Sponsor for safety, behavioural, or administrative reasons.
- The wish of the participant.
- Any intervention related SAEs.
- Anaphylactic reaction following dosing.
- The participant becomes pregnant.

When the target evaluable participant number is achieved, for a given quarantine group or for the overall study, reserve vaccinated participants may not be inoculated with challenge virus. In addition to post vaccination visits (1 and 7 days post vaccination), participants may additionally have assessments performed on Day -2/-1/0 and the final follow up visit Day +155 (± 14 days) for safety and immunogenicity.

Participants who are withdrawn from the study, will be requested to attend an Early Withdrawal Visit, with assessments as detailed in the SoA.

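### Male contraception is required only from quarantine entry, 26–27 days after the single vaccine dose, so Section 5.1 does not provide the safeguard that Section 2.2.1 relies on

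*Combined protocol and SAP*

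**What the plan says.** Section 2.2.1 lists systemic exposure to RSVpreF as a risk. The mitigation is that "male and female participants must be on highly effective contraception methods during the study as described in Section 5.1".

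Section 5.1, criterion 6b, sets the rule for men: "Male participants must agree to the contraceptive requirements below at entry to quarantine and continuing until 28 days after the date of Viral challenge", or after the last dose of investigational product if that is later. It gives the purpose of condom use as "to prevent pregnancy in a female partner or to prevent exposure of any partner (male and female) to the IMP". Criterion 6c adds that "male participants must agree not to donate sperm following discharge from quarantine", with the same end date.

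The timing comes from Section 4.1: "Participants will be randomised to receive a single intramuscular dose of RSVpreF or Placebo on Day -28", with a window of ±3 days, and "Admission to the Quarantine Unit on Day -2/-1". Discharge is planned for Day +12. There is one vaccine dose and no later one. Table 1 in Section 6.1 labels the inoculum "NIMP challenge virus", so it is not investigational product.

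For women of childbearing potential, criterion 6a requires hormonal methods to be established at least two weeks before the first study visit.

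Section 7.2 provides that, once the target number is reached, "reserve vaccinated participants may not be inoculated with challenge virus".

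**The concern.** The male rule exists, in the plan's own words, to prevent pregnancy in a partner and to keep partners from exposure to the investigational product. That product is given once, on Day -28. A rule that first applies on Day -2 or -1 leaves out the weeks straight after the dose, which are the weeks its purpose points to. The rule for women has no such delay, and the plan gives no reason for treating men differently.

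What is at stake is participant and partner protection, and the accuracy of the benefit–risk statement. The risk table tells an ethics committee or regulator that contraception in both sexes mitigates exposure to the vaccine, while the eligibility criteria do not require it of men at that time. The efficacy analysis is not involved.

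**Working it through.** The plan gives no figure for this interval, so there is none to reproduce. The check is study-day arithmetic.

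**Inputs**
- Vaccination: Day -28, window Day -31 to Day -25 (Section 4.1)
- Admission: Day -2 or Day -1 (Section 4.1)
- Planned discharge: Day +12 (Section 4.1)
- Start of male contraception: admission (criterion 6b)
- Start of the sperm-donation rule: discharge (criterion 6c)
- End of both: 28 days after challenge (Day 0) or after the last vaccine dose, whichever is later
- Up to 72 vaccinated, 62 challenged (Section 9.2)

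**1. Dose to start of male contraception** (start day minus vaccination day)

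| Vaccination | Admission Day -2 | Admission Day -1 |
|---|---|---|
| Day -31 | 29 days | 30 days |
| Day -28 | 26 days | 27 days |
| Day -25 | 23 days | 24 days |

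For a man who is challenged, the nominal period from dose to the end of the rule is 28 - (-28) = 56 days. The uncovered share is 26/56 = 46% to 27/56 = 48%, and it is the first part of the period.

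**2. Dose to start of the sperm-donation rule**

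On the text: 12 - (-28) = 40 days. Men are resident in the unit from Day -2/-1 to Day +12, so the interval in which donation is practically possible and not barred is again the 26–27 days before admission.

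**3. A vaccinated man who is not challenged**

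Only the vaccine-based end date applies: -28 + 28 = Day 0.
- Admitted: 0 - (-2) = 2 days or 0 - (-1) = 1 day of cover, out of the 28 days after the dose.
- Across the vaccination window the end date runs from -31 + 28 = Day -3 to -25 + 28 = Day +3. Cover then runs from none (the end date falls before admission) to 3 - (-2) = 5 days.
- Not admitted: the rule has no start date, so cover is 0 days.

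**4. How many this could concern**

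72 - 62 = 10 vaccinated but unchallenged participants under the planning figures. This includes drop-outs and both sexes, and the plan does not give the share of men.

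**5. Does another section close the gap?**

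Section 2.2.1 speaks of contraception throughout the study but refers to Section 5.1 for the rule. The two also disagree at the far end: the study runs to Day +155, and the rule stops 28 days after challenge. Section 8.17.5 collects partner pregnancies, if indicated, from consent; that records them and does not prevent them. No section sets an earlier start for men.

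**The case against.** **The wording may date the agreement and not the use.** Criterion 6b speaks of agreeing at entry, and the Schedule of Activities reviews the applicable criteria at screening, vaccination and admission. Section 2.2.1 could then be read as requiring contraception throughout, with Section 5.1 supplying only the methods. The abstinence option in 6b also refers to the whole risk period of the study treatments. This reading is possible, but it does not rescue the rule: if agreement is first sought at admission, nothing binds a man from Day -28. It also fits poorly with an inclusion criterion, because Section 10.6.1 counts a participant as enrolled at randomisation, which here is the vaccination visit.

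**No harm is shown.** This stands. RSVpreF is a protein antigen given once by intramuscular injection. Section 2 describes studies in pregnant women, up to Phase 3, and reports no safety concerns. No section describes a risk to a partner through semen. This limits the weight of the point but does not remove the mismatch, since the plan itself chose this mitigation.

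**Some supporting details are softer than the main figure.** This also stands. Section 7.2 does not say whether unchallenged reserves are admitted, so the case with no start date is an assumption. The 1–2 days of cover is a nominal figure. The 10 is a planning difference and not a ceiling, because Sections 7.4 and 9.7 allow replacements and up to 5 extra participants per group. The consent form is not in the reviewed text, so whether it repeats the late start is unknown.

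**Conclusion.** The concern holds. As written, criteria 6b and 6c begin after the period they are meant to protect. The gap for men is 26–27 days from the only vaccine dose on the nominal schedule, and 23–30 days across the vaccination window. An admitted but unchallenged man has 1–2 days of cover nominally and 0 to 5 days across the window; one who is never admitted has none.

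This takes the start date in 6b at its word and takes Section 2.2.1 as deferring to Section 5.1. On the alternative reading, that the date concerns only the agreement, men are still not bound from the dose. The result needs no assumption about a biological hazard, and none is claimed. It is a minor safety-drafting correction that should be made. Power, type I error, sample size and the analysis of challenged participants are unaffected.

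**What to change.** - **Criterion 6b:** start the male requirements on the day of vaccination (Day -28) instead of at admission.
- **Criterion 6c:** start the sperm-donation rule on the same day instead of at discharge.
- **End date:** leave it as it is. A challenged man is then covered nominally from Day -28 to Day +28 (56 days), and an unchallenged man for 28 days after the dose. The gap falls to 0 days.
- **Recording:** state that each man's agreement is documented at the vaccination visit before randomisation.
- **Section 2.2.1:** refer to contraception for the period stated in Section 5.1, in place of the whole study.
- **Consent form:** check it and align it where needed.

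The cost is a wording amendment and about four more weeks of contraception for male participants. Visits, sample size and analysis do not change.
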